### **10.1.3 Analysis Methods**

1) Overall Adverse Events, Adverse Drug Reactions and Number of Deaths

(1) The analysis results will be summarized by squamous NSCLC and non-squamous NSCLC separately and totality.

- (2) The number of subjects (incidence rate) of the overall incidence will be provided for all adverse events and adverse drug reactions). The data will be displayed as “subject number (incidence of subjects (%))”.
- (3) The numbers of deaths, subjects with Grade 3 or higher adverse events and adverse drug reactions, and serious adverse events and adverse drug reactions, and discontinuations due to adverse events and adverse drug reactions, and adverse events and adverse drug reactions led to death will be summarized.

## 2) Classification of Adverse Events

- (1) The analysis results will be summarized by squamous NSCLC and non-squamous NSCLC separately and totality.
- (2) Adverse events and adverse drug reactions will be summarized by SOC, PT and CTCAE grade (grade 1, 2, 3, 4, and 5). The data will be displayed as “subject number (incidence of subjects (%))”.
- (3) Incidences of adverse events and adverse drug reactions by SOC and PT will be summarized. In addition, incidences of adverse events and adverse drug reactions will be summarized by SOC, PT and CTCAE grade (any grade, grade 3 or 4, grade 5). And adverse events and adverse drug reactions with an incidence at or above a certain level will be summarized by SOC, PT and CTCAE grade (any grade, grade 3 or 4, grade 5).
- (4) Incidences of adverse events and adverse drug reactions leading to death will be summarized by SOC and PT.
- (5) Incidences of adverse events and adverse drug reactions leading to discontinuation of the study treatment will be summarized by SOC, PT and CTCAE grade (any grade, grade 3 or 4, grade 5).
- (6) Incidences of adverse events and adverse drug reactions leading to interruption of the investigational product will be summarized by SOC, PT and CTCAE grade (any grade, grade 3 or 4, grade 5).
- (7) Incidences of serious adverse events and adverse drug reactions will be summarized by SOC, PT and CTCAE grade (any grade, grade 3 or 4, grade 5).
- (8) Incidences of select adverse events and adverse drug reactions will be summarized by categories, PT and CTCAE grade (any grade, grade 3 or 4, grade 5).
- (9) Incidences of select adverse events and adverse drug reactions leading to discontinuation will be summarized by categories, PT and CTCAE grade (any grade, grade 3 or 4, grade 5).
- (10) Incidences of serious select adverse events will be summarized by categories, PT and CTCAE grade (any grade, grade 3 or 4, grade 5).

(11) Kaplan-Meier curves will be presented for time to onset of select adverse events and adverse drug reactions. Kaplan-Meier curves will also be displayed for time to onset of Grade 3 or higher adverse events and adverse drug reactions.

#### **10.1.4 Subgroup Analysis of Safety Endpoints**

Incidences of select adverse events and adverse drug reactions will be analyzed in subgroups. Risk factors and classification methods using these factors will be based on items established in Section [9.2.5 Subgroup Analysis of Efficacy Endpoint](#). The analysis results will be summarized by squamous NSCLC and non-squamous NSCLC separately and totality.

### **10.2 Clinical Laboratory Evaluation**

#### **10.2.1 Analysis Set**

Analysis will be performed in SAF.

#### **10.2.2 Analysis Items and Data Handling**

##### **1) Analysis Items**

###### **(1) Hematology**

Red blood cell count, mean corpuscular volume (MCV), mean corpuscular hemoglobin (MCH), mean corpuscular hemoglobin concentration (MCHC), hemoglobin, hematocrit, white blood cell count, differential white blood cell count (neutrophils, lymphocytes, eosinophils, basophils, and monocytes), and platelet count.

###### **(2) Blood biochemistry**

Albumin, alkaline phosphatase (ALP), aspartate aminotransferase (AST) (glutamic oxaloacetic transaminase [GOT]), alanine aminotransferase (ALT) (glutamic pyruvic transaminase [GPT]), total bilirubin, direct bilirubin, gamma-glutamyl transpeptidase ( $\gamma$ -GTP), total protein, creatinine, blood glucose, lactate dehydrogenase (LDH), blood urea nitrogen (BUN), uric acid, creatine kinase (CK) (creatinine phosphokinase [CPK]), phosphorus (P), calcium (Ca), sodium (Na), potassium (K), and chloride (Cl).

###### **(3) Urinalysis (qualitative)**

Specific gravity, protein, glucose, occult blood, and sediment (white blood cells and red blood cells).

##### **2) Data Handling**

Data will be analyzed as observed without imputing missing data. The analysis period of clinical laboratory evaluation is treated as well as adverse events.

Any laboratory values that fall below the detection or quantification limit will be imputed to be the detection or quantification limit. The laboratory values will be summarized by Grade, if necessary, according to the National Cancer Institute Common Terminology Criteria for Adverse Events (NCI-CTCAE) version 4.0.

### **10.2.3 Analysis Methods**

- 1) The analysis results will be summarized by squamous NSCLC and non-squamous NSCLC separately and totality.
- 2) For laboratory values and the change from baseline as continuous quantities, summary statistics (no. of subjects, mean, standard deviation, median, minimum, and maximum) will be provided for each laboratory parameter by the time of measurement, while frequency distribution will be created for laboratory values on an ordinal scale.
- 3) Frequency distribution of abnormal laboratory values will be calculated at each time point.
- 4) A Grade shift table will be prepared for changes in hemoglobin, platelet count, white blood cell count, neutrophil count, lymphocyte count, ALT (GPT), AST (GOT), ALP, total bilirubin and creatinine from baseline to the worst value observed during the period from the first dose of the study drug until 28 days after the final dose (or until the start of subsequent anti-cancer therapy for non-small-cell lung cancer after the final dose, whichever comes first).
- 5) Frequency distribution will be calculated for subjects whose liver function test values meet any of the following criteria.
  - (1) ALT or AST > 3 times ULN (Upper Limit of Normal), 5 times ULN, 10 times ULN, 20 times ULN
  - (2) Total bilirubin > 2 times ULN
  - (3) ALT or AST > 3 times ULN and total bilirubin within 1 day > 2 times ULN
  - (4) ALT or AST > 3 times ULN and total bilirubin within 30 days > 2 times ULN
  - (5) ALT or AST > 3 times ULN, total bilirubin within 1 day  $\geq$  2 times ULN, and ALP < 2 times ULN

## **10.3 Immunologic Test**

### **10.3.1 Analysis Set**

Analysis will be performed in SAF.

### **10.3.2 Analysis Items and Data Handling**

- 1) Analysis Items

Rheumatoid factor (RA), C-reactive protein (CRP), antinuclear antibody (ANA), SP-D, and KL-6.

## 2) Data Handling

Data will be analyzed as observed without imputing missing data. The analysis period of immunologic test is treated as well as adverse events.

Any immunologic test values that fall below the detection or quantification limit will be imputed to be the detection or quantification limit.

### **10.3.3 Analysis Methods**

- 1) Summary statistics (no. of subjects, mean, standard deviation, median, minimum, and maximum) will be provided for immunologic test values and the change from baseline as continuous quantities, while frequency distribution will be created for those on an ordinal scale.
- 2) Frequency distribution of abnormal immunologic test values will be calculated at each time point.
- 3) The analysis results will be summarized by squamous NSCLC and non-squamous NSCLC separately and totality.

## **10.4 Hormonal Test**

### **10.4.1 Analysis Set**

Analysis will be performed in SAF.

### **10.4.2 Analysis Items and Data Handling**

#### 1) Analysis Items

Thyroid-stimulating hormone (TSH), free triiodothyronine (free T3), and free thyroxine (free T4).

#### 2) Data Handling

Data will be analyzed as observed without imputing missing data. The analysis period of hormonal test is treated as well as adverse events.

Any hormonal test values that fall below the detection or quantification limit will be imputed to be the detection or quantification limit.

### **10.4.3 Analysis Methods**

- 1) The analysis results will be summarized by squamous NSCLC and non-squamous NSCLC separately and totality.
- 2) Summary statistics (no. of subjects, mean, standard deviation, median, minimum, and maximum) will be provided for each hormonal test parameter value and the change from baseline by the time of measurement.

- 3) Frequency distribution of abnormal hormonal test values will be calculated at each time point.
- 4) Frequency distribution will be calculated for subjects whose thyroid function test values meet any of the following criteria.
  - (1)  $TSH > ULN$
  - (2)  $TSH > ULN$  with  $TSH \leq ULB$  at Baseline
  - (3)  $TSH > ULN$  with at least one  $FT3/FT4$  test values  $< LLN$  (Lower Limit of Normal)
  - (4)  $TSH > ULN$  with all other  $FT3/FT4$  test values  $\geq LLN$
  - (5)  $TSH > ULN$  with  $FT3/FT4$  test missing
  - (6)  $TSH < LLN$
  - (7)  $TSH < LLN$  with  $TSH \geq LLN$  at Baseline
  - (8)  $TSH < LLN$  with at least one  $FT3/FT4$  test values  $> ULN$
  - (9)  $TSH < LLN$  with all other  $FT3/FT4$  test values  $\leq ULN$
  - (10)  $TSH < LLN$  with  $FT3/FT4$  test missing

## **10.5 Vital Signs**

### **10.5.1 Analysis Set**

Analysis will be performed in SAF.

### **10.5.2 Analysis Items and Data Handling**

#### 1) Analysis Items

Systolic blood pressure/diastolic blood pressure, pulse rate, temperature, weight, and percutaneous oxygen saturation as measured using pulse oximetry ( $SpO_2$ ).

#### 2) Data Handling

Data will be analyzed as observed without imputing missing data.

### **10.5.3 Analysis Methods**

Summary statistics (no. of subjects, mean, standard deviation, median, minimum, and maximum) will be provided for each vital sign parameter by the time of measurement. The analysis results will be summarized by squamous NSCLC and non-squamous NSCLC separately and totality.

## **10.6 12-lead ECG**

### **10.6.1 Analysis Set**

Analysis will be performed in SAF.

## 10.6.2 Analysis Items and Data Handling

### 1) Analysis Items

Heart rate, RR interval, QT interval, QTcF, PR interval, QRS width.

### 2) Data Handling

12-lead ECG data will be analyzed as observed without imputing missing data.

QTcF will be calculated using the following compensation formula.

$$\text{QTcF (ms)} = \text{QT interval} / (\text{RR interval})^{1/3}.$$

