	Section 10.1.3 2) (6) "Incidences of adverse events and adverse drug reactions leading to interruption of the investigational product will be summarized by SOC and PT."	Changed to: "Incidences of adverse events and adverse drug reactions leading to interruption of the investigational product will be summarized by SOC, PT and CTCAE grade (any grade, grade 3 or 4, grade 5)."	Add for evaluating the safety in more detail.

	Section 10.1.3 2) (7) “Incidences of serious adverse events and adverse drug reactions will be summarized by SOC and PT.”	Changed to: “Incidences of serious adverse events and adverse drug reactions will be summarized by SOC, PT and CTCAE grade (any grade, grade 3 or 4, grade 5).”	Add for evaluating the safety in more detail.
	Section 10.1.3 2) (8) “Incidences of select, Grade 3 or higher, adverse events and adverse drug reactions will be summarized by categories and PT.”	Changed to: “Incidences of select adverse events and adverse drug reactions will be summarized by categories, PT and CTCAE grade (any grade, grade 3 or 4, grade 5).”	Add for evaluating the safety in more detail.
	Section 10.1.3 2)	Added: “(9) Incidences of select adverse events and adverse drug reactions leading to discontinuation will be summarized by categories, PT and CTCAE grade (any grade, grade 3 or 4, grade 5). (10) Incidences of serious select adverse events will be summarized by categories, PT and CTCAE grade (any grade, grade 3 or 4, grade 5).”	Add for evaluating the safety in more detail.
	Section 10.1.4	Added: “and totality”	Add for clarification.
	Section 10.2.3	Added: “and the change from baseline”	Add for evaluating the safety in more detail.
	Section 10.3.3 1)	Added: “and the change from baseline”	Add for evaluating the safety in more detail.
	Section 10.3.3 3)	Added: “and totality”	Add for clarification.
	Section 10.4.3 2) “Summary statistics (no. of subjects, mean, standard deviation, median, minimum, and maximum) will be provided for each Hormonal test parameter by the time of measurement.”	Changed to: “Summary statistics (no. of subjects, mean, standard deviation, median, minimum, and maximum) will be provided for each hormonal test parameter value and the change from baseline by the time of measurement.”	Add for evaluating the safety in more detail.
	Section 10.6.2 2)	Added: QTcF will be calculated using the following compensation formula. QTcF (ms) = QT interval / (RR interval) 1/3 .	Add the formula.

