## LIST OF ABBREVIATIONS AND DEFINITIONS OF TERMS

ADAS	Anti-drug Antibody Analysis Set
ALK	Anaplastic Lymphoma Kinase
ALP	alkaline phosphatase
ALT (GPT)	Alanine aminotransferase (glutamic pyruvic transaminase)
ANA	anti-nuclear antibody
AST (GOT)	Aspartate aminotransferase (glutamate oxaloacetate transaminase)
BMI	body mass index
BUN	blood urea nitrogen
CK (CPK)	creatinine kinase (creatinine phosphokinase)
Cl	Chloride
CR	complete response
CRP	C-reactive protein
CT	computed tomography
CTCAE	Common Terminology Criteria for Adverse Events
CTLA-4	cytotoxic T lymphocyte-associated antigen 4
DNA	deoxyribonucleic acid
ECOG	Eastern Cooperative Oncology Group
eCRF	electronic case report form
EGFR	epidermal growth factor receptor
FAS	full analysis set
G-CSF	granulocyte colony stimulating factor
GH	growth hormone
HBc	hepatitis B virus core protein
HBs	hepatitis B virus surface protein
HBV	hepatitis B virus
HCV	hepatitis C virus
HIV-1	human immunodeficiency virus-1
HIV-2	human immunodeficiency virus-2
HLA	human leukocyte antigen
IL	interleukin
IP	interferon-inducible protein
LDH	Lactate dehydrogenase
MCH	mean corpuscular hemoglobin

MCHC	mean corpuscular hemoglobin concentration
MCV	mean corpuscular volume
NCI	National Cancer Institute, United States
NE	not evaluable
NKT cell	natural killer T cell
NYHA	New York Heart Association
PD	progressive disease
PD-1	Programmed cell death-1
PD-L1	Programmed cell death-ligand 1
PD-L2	Programmed cell death-ligand 2
Performance Status	Performance Status
PR	partial response
PT	preferred term
QRS	ventricular activation time
QT	electrocardiogram QT interval (electrical ventricular contraction time)
QTcF	QT interval corrected for heart rate according to Fridericia's formula
RA	rheumatoid factor
RANKL	Receptor activator of NF- $\kappa$ B ligand
RECIST	Response Evaluation Criteria in Solid Tumors
RNA	ribonucleic acid
SAF	Safety Analysis Set
SD	stable disease
SOC	System Organ Class
SP-D	pulmonary surfactant protein D
SpO 2	percutaneous oxygen saturation
TSH	thyroid stimulating hormone
UICC-TNM	Union Internationale Contre Le Cancer TNM
$\gamma$ -GTP	Gamma-glutamyltranspeptidase

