## 10.6.3 Analysis Methods

- 1) The analysis results will be summarized by squamous NSCLC and non-squamous NSCLC separately and totality.
- 2) For 12-lead ECG parameters (observed values of RR interval, QT interval, Fridericia's corrected QT interval [QTcF], QRS width, and PR interval, and their changes from baseline [ $\Delta$ QTcF,  $\Delta$ QRS, and  $\Delta$ PR]), observed value (HR) and change from baseline ( $\Delta$ HR) of heart rate, summary statistics and frequency distribution for each category will be summarized at each time point.
- 3) For maximum QTcF, maximum  $\Delta$ QTcF, maximum QRS, maximum PR, and maximum heart rate of subjects, frequency distribution for each category will be calculated.

Item	Classification
RR (ms) (observed value)	$\leq 600$ , $> 600\text{--}1200$ , $> 1200$
PR (ms) (observed value)	$\leq 120$ , $> 120\text{--}200$ , $> 200$
QRS (ms) (observed value)	$\leq 60$ , $> 60\text{--}109$ , $> 109$
Heart rate (observed value)	$\leq 50$ , $> 50\text{--}100$ , $> 100$
QT interval, QTcF (ms) (observed value)	$\leq 450$ , $> 450\text{--}480$ $> 480\text{--}500$ , $> 500$
$\Delta$ QTcF (ms) (change from baseline)	$\leq 30$ , $> 30\text{--}60$ , $> 60$

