### 12.3 Decimals

When displaying the individual data, the number of significant figures will be as shown below. For the mean, standard deviation, and median, the number of significant figures will be the number of significant figures for the individual data + 1. For example, if the number of significant decimal places for individual items of data is 1, that for the mean, standard deviation, and median will be 2.

- Background factors and efficacy endpoint

Integer value (No decimal places)	One decimal place	Two decimal places
Time from diagnosis date of primary disease to first dose date of the investigational product (days) Age (years)	Height (cm) Weight (kg) BMI (kg/m  )	Percent change in tumor diameter of target lesion (%)

· Laboratory values

Integer value (No decimal places)	One decimal place
White blood cell count (/mm  )	MCH (pg)
Red blood cell count (10  /mm  )	MCHC (%)
MCV (fL)	Hemoglobin (g/dL)
AST (GOT) (U/L)	Hematocrit (%)
ALT (GPT) (U/L)	Platelet count (10  /mm  )
ALP (U/L)	Albumin (g/dL)
γ-GTP (U/L)	Total protein (g/dL)
LDH (U/L)	Total bilirubin (mg/dL)
CK (CPK) (U/L)	Direct bilirubin (mg/dL)
Blood glucose (mg/dL)	Uric acid (mg/dL)
BUN (mg/dL)	K (mEq/L)
Na (mEq/L)	Ca (mEq/L)
Cl (mEq/L)	P (mEq/L)
Neutrophil (/mm  )	CRP (mg/dL)
Lymphocyte (/mm  )	SP-D (ng/mL)
Eosinophil (/mm  )	
Basophil (/mm  )	
Monocyte (/mm  )	
RA (IU/mL)	
KL-6 (U/mL)	
Two decimal places	
Three decimal places	
Creatinine (mg/dL)	Urine specific gravity
Free triiodothyronine (pg/mL)	Thyroid-stimulating hormone (μIU/mL)
Free thyroxine (ng/dL)	

· Vital signs

Integer value (No decimal places)	One decimal place
Systolic blood pressure (mmHg)	Temperature (°C)
Diastolic blood pressure (mmHg)	SpO 2 (%)
Pulse rate (bpm)	

· 12-lead ECG

Integer value (No decimal places)
Heart rate (beats/min)
RR interval (ms)
QT interval (ms)
QTcF (ms)
PR interval (ms)
QRS width (ms)

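### Does the missing unit for RR in the SAP's QTcF formula put the ECG tables at risk?

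*SAP*

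**What the plan says.** SAP 10.6.2 lists the ECG items without units: "Heart rate, RR interval, QT interval, QTcF, PR interval, QRS width". Under data handling it states that "QTcF will be calculated using the following compensation formula" and prints QT divided by the cube root of RR. The left-hand side carries ms; neither input carries a unit, and no conversion is shown. The History of Revision records the addition of the same expression, beginning "QTcF (ms) = QT interval / (RR interval", so no conversion factor was lost when the current text was read from PDF.

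RR has a unit in two other places, and both times it is ms. The class table in SAP 10.6.3 has the row "RR (ms) (observed value" with cut points at 600 and 1200, and the decimals table in SAP 12.3 lists "RR interval (ms" among the whole-number items.

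The method is named. The List of Abbreviations defines QTcF as "QT interval corrected for heart rate according to Fridericia", followed by the word formula, and 10.6.3 repeats the name. The class table puts QT and QTcF in one row, "QT interval, QTcF (ms) (observed value", with shared limits at 450, 480 and 500. Change in QTcF is classed at 30 and 60 ms. Item 3 of 10.6.3, which opens "For maximum QTcF, maximum", asks for the same classes on each subject's largest value.

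**The concern.** A formula in an analysis plan should work in the units of the data that go into it. Here the result depends on the unit of one input, that unit is missing, and the only RR unit printed anywhere in the SAP is the one that gives a wrong answer. A programmer who took the line literally and applied it to an RR variable stored in ms would obtain values around 40 where about 400 is expected.

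At stake are the QTcF safety tables. On the shrunken scale the class limits could hardly be reached, so the tables by time point and the tables of per-subject maxima would show no QT prolongation whatever the data held. This matters because the line was added in an amendment expressly to specify the derivation.

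**Working it through.** The documents give no worked QTcF value, so there is no figure to reproduce. The check is what the formula yields under each unit, and which unit the rest of the SAP allows.

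**Inputs.** The formula is from SAP 10.6.2. The RR limits (600 and 1200 ms), the QT/QTcF limits (450, 480 and 500 ms) and the change limits (30 and 60 ms) are from the class table in 10.6.3. The RR limits match the heart-rate limits in the same table: 60,000/600 = 100 and 60,000/1200 = 50 beats per minute. RR from 600 to 1200 ms is therefore the SAP's own middle range.

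**Ratio of the two readings.**

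- Seconds: QT / (RR/1000)^(1/3)
- Milliseconds: QT / RR^(1/3)
- Ratio, ms reading to seconds reading: 1 / 1000^(1/3) = 1/10, for every QT and RR

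**Values at the SAP's cut points (all in ms).**

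| RR | QT | QTcF, RR in seconds | QTcF, RR in ms |
|---|---|---|---|
| 600 | 450 | 533.5 | 53.4 |
| 600 | 480 | 569.1 | 56.9 |
| 600 | 500 | 592.8 | 59.3 |
| 1200 | 450 | 423.5 | 42.3 |
| 1200 | 480 | 451.7 | 45.2 |
| 1200 | 500 | 470.5 | 47.1 |

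**Effect on the classes under the ms reading.**

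- To leave the lowest QTcF class, the true value would have to exceed 450 × 10 = 4,500 ms.
- To leave the lowest change class, the true change would have to exceed 30 × 10 = 300 ms; to reach the highest, 60 × 10 = 600 ms.
- In terms of raw QT, passing 450 would need about 3,795 ms at RR 600, 4,500 ms at RR 1000 and 4,782 ms at RR 1200.

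**Which unit fits the SAP.** The shared QT/QTcF row makes sense only if the correction leaves QT on roughly its own scale, that is, if the divisor is near 1. Over RR 600 to 1200 ms:

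- in seconds, the divisor runs from 0.6^(1/3) = 0.843 to 1.2^(1/3) = 1.063;
- in ms, it runs from 600^(1/3) = 8.43 to 1200^(1/3) = 10.63.

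Only seconds fits. At RR 1000 ms the divisor in seconds is exactly 1, and QT 400 gives QTcF 400. The ms reading gives 40, on a scale for which the SAP has no usable class. The table and the named method therefore point to the same unit.

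**The case for a change.** The strongest case for a change is that a formula added in order to specify a derivation should be complete. It states the unit of its result and not of its inputs, the SAP shows RR only in ms, and a literal program would empty every class that could signal prolongation. The cost of stating the unit is one line.

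Part of this stands. The unit is missing, the factor of ten is exact, and stating the unit would be tidier. The rest does not carry the weight put on it. The ms labels in 10.6.3 and 12.3 govern classification and decimal places, and no sentence makes them the formula's input. Nor is the programmer left without guidance: the method is named in two places, its usual printed form is the one shown, and the class limits exclude the other reading.

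The slip would also not stay hidden. SAP 10.6.3 requires summary statistics for both QT and QTcF at each time point, so a mean QT near 400 would appear with a mean QTcF near 40.

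**Conclusion.** No change to the plan is needed. This is a missing unit label in a descriptive safety derivation, and no figure in the documents is miscalculated. An analyst who follows the named correction enters RR in seconds and obtains sound values, so the error on the intended reading is zero. The tenfold error arises only if the formula is coded literally, on RR in ms, and the result then passes unnoticed. Nothing in the documents shows that this happened.

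Even then the reach would be narrow. SAP 12.2 provides for no significance tests, the primary response rate and the sample size do not use ECG data, and no QTcF limit appears among the discontinuation criteria in SAP 3.6 or protocol section 7.

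The conclusion rests on two assumptions: that Fridericia's correction is applied in its standard form, with RR in seconds, and that the tables receive an ordinary plausibility check. The shared QT/QTcF classes support the first from within the SAP. Writing the unit into the formula would be harmless tidying and would alter no correctly programmed result.
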